### ***3.1.6      Stopping Rule for Dose Escalation Cohort***

During the dose escalation phase, if more than one drug-related Grade 4 toxicity or drug-related death occurs at a dose level for a specific cohort, new subject accrual in that cohort at that dose level will be held. A discussion with investigators may be held to review the risk/benefit of this regimen. This discussion will be triggered if the following criteria are met:

- Majority of subjects who discontinue due to treatment related AEs have deep tumor response (ie, > 80% reduction)
- All treatment related AEs leading to discontinuation are non-fatal, reversible and without severe sequela (ie, GI perforation)
- Majority of the treatment related AEs are laboratory in nature, asymptomatic, and readily monitored with routine blood draws.

If a decision is made to continue with a dose level because of a favorable risk/benefit profile despite meeting the ‘not tolerable’ criteria (‘more than one drug-related Grade 4 toxicity or drug-related death’), then IRBs must be notified, ICFs must be updated, and discussion of the risk/benefit must be documented with all future subjects who enroll on this regimen.

### **3.1.7     *Stopping Rules for Clinical Deterioration***

Clinical deterioration will be assessed to have occurred after a clinical event that, in the Investigator’s opinion, is attributable to disease progression, is unlikely to reverse with continued study treatment and therefore indicates that the subject is not benefiting from study treatment and cannot be managed by the addition of supportive care (such as bisphosphonates and/or bone directed radiotherapy, thoracentesis or paracentesis of accumulating effusions). The decision to continue or stop treatment should be discussed with the BMS Medical Monitor and will be documented in the study files.

Examples of events that may, in the Investigator’s opinion, indicate a lack of clinical benefit include, but are not limited to, the following:

- Performance status decrease of at least 2 points from baseline
- Skeletal related events defined by the following:
  - Pathologic bone fracture in the region of cancer involvement
  - Cancer related surgery to bone
  - Spinal cord or nerve root compression
- Bladder outlet or urethral obstruction
- Development of new central nervous system metastases or  $\geq$  Grade 3 encephalopathy
- Any setting where the initiation of new anti-neoplastic therapy has been deemed beneficial to the subject.

### **3.1.8     *Treatment Beyond Progression for Nivolumab or Nivolumab plus Ipilimumab***

Accumulating clinical evidence indicates some subjects treated with immune system stimulating agents may develop disease progression by conventional response criteria before demonstrating clinical objective responses and/or stable disease. This phenomenon was observed in the Phase 1 study of nivolumab, CA209003, and confirmed in multiple Phase 3 studies (ie, lung CA209017; melanoma CA209037, CA209066, and CA209067). Two hypotheses explain this phenomenon. First, enhanced inflammation within tumors could lead to an increase in tumor size which would

appear as enlarged index lesions and as newly visible small non-index lesions. Over time, both the malignant and inflammatory portions of the mass may then decrease leading to overt signs of clinical improvement. Alternatively, in some individuals, the kinetics of tumor growth may initially outpace anti-tumor immune activity. With sufficient time, the anti-tumor activity will dominate and become clinically apparent. Therefore, subjects will be allowed to continue study therapy after an initial investigator-assessed RECIST 1.1 ([Appendix 2](#)) defined progression as long as they meet the following criteria:

- Investigator assessed clinical benefit
- Subject is tolerating nivolumab or nivolumab plus ipilimumab
- Treatment beyond progression will not delay an imminent intervention to prevent serious complications of disease progression (eg, CNS metastases)
- Subject provides written informed consent prior to receiving any additional nivolumab or nivolumab plus ipilimumab treatment, using an ICF describing any reasonably foreseeable risks or discomforts, or other alternative treatment options.

These criteria aim to ensure the risk/benefit for continuing treatment will continue to favor the subjects. The assessment of clinical benefit should take into account whether the subject is clinically deteriorating and unlikely to receive further benefit from continued treatment. The decision to continue treatment beyond initial investigator-assessed progression should be discussed with the BMS Medical Monitor and documented in the study records.

If the decision is taken to continue nivolumab treatment beyond progression, the subject will remain on the trial and continue to be treated and monitored according to the Time and Events Schedule in [Table 5.1-4](#), [Table 5.1-5](#) and, [Table 5.1-7](#).

Subjects should discontinue study therapy upon further evidence of further progression, defined as an additional 10% or greater increase in tumor burden SLD from time of initial progression (including all target lesions and new measurable lesions). New lesions are considered measurable if the longest diameter is at least 10 mm (except for pathological lymph nodes, which must have a short axis of at least 15 mm). Any new lesion considered non-measurable may become measurable and therefore included in the tumor burden measurement if the longest diameter increases to at least 10 mm (except for pathological lymph nodes, which must have an increase in short axis to at least 15 mm). Nivolumab treatment should be discontinued permanently upon documentation of further progression.

For statistical analyses that include the investigator-assessed progression date, subjects who continue treatment beyond initial investigator-assessed, RECIST 1.1-defined progression will be considered to have investigator-assessed progressive disease at the time of the initial progression event.

For subjects discontinuing treatment because of global deterioration of health status without objective evidence of disease progression at that time, progression should be reported as “symptomatic deterioration”. Every effort should be made to document objective progression (ie, radiographic confirmation) even after discontinuation of treatment.

### **3.2 Post Study Access Therapy**

At the conclusion of the study, subjects who continue to demonstrate clinical benefit will be eligible to receive BMS supplied study drug. Study drug will be provided via an extension of the study, a rollover study requiring approval by responsible health authority and ethics committee or through another mechanism at the discretion of BMS. BMS reserves the right to terminate access to BMS supplied study drug if any of the following occur: a) the marketing application is rejected by responsible health authority; b) the study is terminated due to safety concerns; c) the subject can obtain medication from a government sponsored or private health program; or d) therapeutic alternatives become available in the local market.

### **3.3 Study Population**

For entry into the study, the following criteria MUST be met. Eligibility criteria for this study have been carefully considered to ensure the safety of the study subjects and to ensure that the results of the study can be used. It is imperative that subjects fully meet all eligibility criteria. No exceptions will be granted.

For entry into the study, the following criteria MUST be met.

#### **3.3.1 Dose Escalation and Expansion Phase**

##### **3.3.1.1 Inclusion Criteria**

###### **1. Signed Written Informed Consent**

- a) The signed informed consent form prior to the performance of any study related procedures that are not considered part of standard of care.

###### **2. Target Population**

- a) Subjects with advanced hepatocellular carcinoma not amenable for management with curative intent by surgery or local therapeutic measures.
- b) Histological confirmation of hepatocellular carcinoma. Subjects with radiological diagnosis may be enrolled for screening in the study but histological confirmation is mandatory prior to initiation of study therapy.
- c) Subjects must fulfill the criteria for prior therapy as follows:
  - i) For the dose escalation cohorts (uninfected, HCV-infected, and HBV-infected), subjects must have progressive disease following or be intolerant of at least one line of systemic therapy or refuse sorafenib treatment (refusal must be documented); subjects cannot be on active cancer therapy during the screening period.
  - ii) For the uninfected sorafenib progressors in the Expansion Phase, subjects must have had documented radiographic or symptomatic progression during or after sorafenib therapy
  - iii) For the uninfected sorafenib naive or intolerant subjects in the Expansion Phase, subjects must either have never received sorafenib treatment or were intolerant to sorafenib therapy as defined in [Section 1.4.9](#).
  - iv) For the HCV and HBV cohorts in the Expansion Phase, subjects must have received sorafenib treatment and be either intolerant or have had documented radiographic or symptomatic progression during or after sorafenib therapy as defined in [Section 1.4.9](#).

- d) Subjects must have Child-Pugh scores as follows ([Appendix 3](#)):
  - i) Dose Escalation Phase: Child-Pugh score of 7 points or less, ie, Child-Pugh A or Child Pugh B7.
  - ii) Expansion Phase: Child-Pugh score of 6 points or less, ie, Child-Pugh A.
- e) Eastern Cooperative Oncology Group (ECOG) Performance Status of 0 to 1 ([Appendix 4](#));
- f) The noninfected HCC arm Dose Escalation Phase and Expansion Phase will include subjects with prior HCV or HBV infection provided there is no active viral replication (negative for HBV DNA and/or HBV surface antigen and HCV RNA). HBV exposed subjects with resolved HBV infection who have seroconverted must have detectable HBsAb and HBcAb titers and have undetectable HBsAg and HBV DNA.
- g) In the Dose Escalation Phase and Expansion Phase, the HCV infected arm must have evidence of HCV RNA. Subjects may have evidence of prior HBV infection but must have detectable HBsAb and HBcAb titers and have undetectable HBsAg and HBV DNA.
- h) In the Dose Escalation Phase and Expansion Phase, subjects with chronic HBV infection must have evidence of ongoing viral replication (detectable HBsAg, HBeAg, or HBV DNA). Subjects with chronic HBV infection must have HBV DNA viral load < 100 IU/mL at screening. In addition, they must be on antiviral therapy per regional standard of care guidelines prior to initiation of study therapy. If not on antiviral therapy at screening, then the subject must initiate treatment per regional standard of care guidelines at the time of consent. All subjects enrolled in the HBV cohort must continue antiviral therapy through follow-up visit 2. Both HBeAg positive and negative subjects will be included.
  - i) All subjects must have at least one measurable lesion.
  - j) For subjects in the Dose Escalation Phase and Expansion Phase, the lesion can be accurately measured by CT-scan ( $\geq 10$  mm) according to RECIST1.1 (malignant lymph nodes must be  $> 15$  mm on short axis) (additional details are included in [Appendix 2](#))
    - i) Previously treated lesions can be considered target lesions if there is clear evidence of progression.
    - ii) Bone metastases are not considered measurable lesions, unless there is a measurable soft tissue component per RECIST1.1.
    - iii) The measurable lesion cannot be biopsied during treatment (if there is only one lesion).
  - k) A formalin fixed, paraffin-embedded (FFPE) tumor tissue block or unstained slides of tumor sample (archival or recent) must be available for biomarker evaluation, as described in [Section 5.6](#).
    - i) Subjects must consent to allow the acquisition of existing formalin-fixed paraffin-embedded (FFPE) material (block or a minimum of 15 unstained slides) for performance of correlative studies; attempts should be made to collect at least 20 unstained slides.
    - ii) If archived samples are not available, the subject must provide a fresh biopsy sample at screening - for this biopsy, subjects must have a soft tissue tumor lesion that can be biopsied at acceptable clinical risk (as judged by the investigator) at baseline.

Subjects must consent to the pre-treatment fresh biopsy (if no archived samples are available) as a condition of protocol participation. In this setting, if adequate tissue is not obtained during the first procedure then a repeat biopsy should be considered based on the investigator's assessment of clinical risk. However, a repeat biopsy is not required to meet eligibility. Optional post treatment biopsy may or may not be obtained, depending on procedures specific at each study site.

- iii) Lesions selected for biopsy should be large enough to allow for the collection of tumor tissue using a minimum 18 gauge or larger needle with an expected core sample length of 5 mm. A minimum of 2 passages of the needle core should be obtained. If adequate tissue is not obtained following initial passages of the needles, repeat passages of the needle should be performed if clinically feasible. Smaller lesions may be biopsied or smaller gauge needles may be used provided adequate tissue can be collected (similar quantity to amount collected using 18 gauge thickness and 5 mm core length).
- iv) The immediate confirmation (eg, touch imprint cytopathology) for presence of viable tumor cells from collected tissue samples is strongly recommended.
- l) Adequate organ and marrow function as evidenced by:
  - i) WBC  $\geq 2000/\mu\text{L}$  (stable, off any growth factor within 4 weeks of study drug administration)
  - ii) Neutrophils  $\geq 1000/\mu\text{L}$  (stable, off any growth factor within 4 weeks of study drug administration)
  - iii) Platelets  $\geq 60 \times 10^3/\mu\text{L}$  (transfusion to achieve this level is not permitted)
  - iv) Hemoglobin  $\geq 9.0 \text{ g/dL}$  (may be transfused to meet this requirement)
  - v) Creatinine CrCl  $>40 \text{ mL/min}$  (Cockcroft-Gault formula)
  - vi) AST  $\leq 5 \times \text{ULN}$
  - vii) ALT  $\leq 5 \times \text{ULN}$
  - viii) Bilirubin  $\leq 3 \text{ mg/dL}$
  - ix) INR  $\leq 2.3$  or Prothrombin time (PT)  $\leq 6 \text{ seconds above control}$
  - x) Albumin  $\geq 2.8 \text{ g/dL}$
- m) Ability to comply with treatment, PK and immune-monitoring sample collection (when indicated) and required study follow-up.

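### Inclusion criteria 2(f) and 2(h) contradict each other on HBV markers, so some subjects fit both the noninfected and the HBV cohort

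*Combined protocol and SAP*

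**What the plan says.** Protocol Section 3.3.1.1, Target Population, sets the cohort definitions for the Dose Escalation and Expansion Phases.

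- **Item (f), noninfected arm.** It may include "subjects with prior HCV or HBV infection provided there is no active viral replication", and the bracket that follows explains this as "negative for HBV DNA and/or HBV surface antigen and HCV RNA". The next sentence adds that "HBV exposed subjects with resolved HBV infection who have seroconverted must have detectable HBsAb and HBcAb titers" and "have undetectable HBsAg and HBV DNA".
- **Item (g), HCV arm.** Subjects with past HBV infection must have both HBsAg and HBV DNA undetectable.
- **Item (h), HBV arm.** It states that "subjects with chronic HBV infection must have evidence of ongoing viral replication (detectable HBsAg, HBeAg, or HBV DNA", so any one of the three markers is enough. It also says "Subjects with chronic HBV infection must have HBV DNA viral load < 100 IU/mL at screening" and that "they must be on antiviral therapy per regional standard of care guidelines prior to initiation of study therapy". Subjects not yet on antivirals start them at consent. A separate sentence requires those enrolled in the HBV cohort to stay on antivirals through follow-up visit 2.

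The Synopsis and Section 1.1.2 describe the uninfected group as having no active hepatitis virus infection.

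**The concern.** The cohorts are meant to be mutually exclusive by etiology, yet 'and/or' lets one negative HBV marker stand in for two. The pattern most exposed is HBsAg-positive with undetectable DNA. Item (h) makes this pattern foreseeable, because it requires low DNA and antiviral therapy in its own cohort.

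The label matters for four reasons.

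- **Dose.** In escalation, the noninfected arm started at 0.3 mg/kg with a maximum of 10 mg/kg. The HBV arm started at 0.1 mg/kg with a maximum of 3 mg/kg (Sections 1.1.2, 3.1 and 3.1.3).
- **Entry.** In Expansion, sorafenib-naive subjects are eligible for a noninfected cohort under 2(c)(iii) but not for the HBV cohort under 2(c)(iv).
- **Antiviral continuation.** This duty is written for subjects enrolled in the HBV cohort.
- **Interpretation.** The Synopsis gives HBV infection as the reason to expect the highest hepatic risk, even after clearance by standard assays. Hepatic safety by etiology therefore depends on a clean label.

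**Working it through.** **1. Marker patterns.** Inputs are items (f) and (h). HCV RNA is taken as negative throughout, and the HCV RNA condition in (f) is taken to apply whichever HBV reading is used. The two readings are:

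- (f) under 'or': DNA negative or HBsAg negative
- (f) under 'and': DNA negative and HBsAg negative
- (h): HBsAg, HBeAg or DNA detectable

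| HBsAg | HBV DNA | HBeAg | (f) 'or' | (f) 'and' | (h) |
|---|---|---|---|---|---|
| − | − | − | yes | yes | no |
| − | − | + | yes | yes | yes |
| − | + | − | yes | no | yes |
| − | + | + | yes | no | yes |
| + | − | − | yes | no | yes |
| + | − | + | yes | no | yes |
| + | + | − | no | no | yes |
| + | + | + | no | no | yes |

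Under 'or', 5 of 8 patterns meet both definitions. Under 'and', 1 of 8 does: isolated HBeAg positivity, which remains because (f) never mentions HBeAg. These are counts of patterns and say nothing about how many subjects show each one.

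**2. Does the second sentence of (f) close the gap?** It demands both markers undetectable, but only for resolved, seroconverted infection. An HBsAg-positive subject is not in that group, so the sentence does not exclude such a subject.

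**3. Which antiviral duties depend on the label?** Item (h) attaches the DNA ceiling and the antiviral-at-entry rule to subjects with chronic HBV infection, without naming a cohort. Only continuation through follow-up visit 2 is attached to enrolment in the HBV cohort.

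**4. Effect on ORR.** The plan's own figure comes first: 10 responders of 50, with a stated 95% Clopper-Pearson lower bound of 10%. The lower limit is the 0.025 quantile of Beta(10, 41), which is 10.03%. The upper limit is the 0.975 quantile of Beta(11, 40), which is 33.72%. The stated bound reproduces.

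Now suppose k of 50 subjects in a noninfected cohort are misassigned. Take an ORR of 20% for correctly assigned subjects (the plan's illustration) and 14% for the others (an assumption with no source in the documents). The shift is k/50 × (20 − 14) points:

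- k = 0: 0 points
- k = 5: 0.1 × 6 = 0.6 points (0.9 × 20% + 0.1 × 14% = 19.4%)
- k = 10: 0.2 × 6 = 1.2 points (18.8%)

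If the 14% were replaced by 0%, the extreme downward case, k = 10 would give 0.2 × 20 = 4 points. The exact interval above reaches about 10 points below the 20% estimate.

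**The case against.** The best defence is that the protocol already supplies the right reading. The controlling words of (f) are prior infection without active replication, and (h) says what replication evidence is. An HBsAg-positive subject then has replication by the protocol's own terms and fails (f). Item (g), the second sentence of (f), and the chronic-HBV definitions for the later cohorts (Sections 3.3.2.1 and 3.3.3.1) all fit 'and'. This stands as evidence of intent, and a reader who infers that the protocol plainly permits HBsAg-positive subjects to enter as noninfected goes too far. It does not remove the defect. The bracket with 'and/or' is the explanation (f) itself gives of no active replication, and Section 3.3 tells sites to apply the criteria without exception.

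A reader might also infer that such subjects would have no required antiviral cover. The text does not support that. The entry rules in (h) follow infection status and arguably bind them in any arm, and Section 3.4.4 provides for ongoing HBV DNA assessment without limiting it to the HBV cohort. What remains is the continuation duty, and the practical risk that a site which labels a subject noninfected does not consult (h) at all.

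Finally, the documents do not show that anyone was misassigned, and the ORR arithmetic rests on assumed inputs. Both points are right.

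**Conclusion.** The point holds as a contradiction between 2(f) and 2(h) that leaves two etiologic cohorts overlapping on a literal reading. It is minor. Any consequence for data or subjects is conditional on a site having used 'or', which the documents neither show nor rule out.

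On the assumed rates and 0 to 10 misassigned of 50, the ORR shift is 0 to 1.2 points. That is small beside the sampling uncertainty of a 50-subject cohort, and a claim of material ORR bias is not supported. The more important consequence is that hepatic events in HBsAg-positive subjects could be counted under the noninfected label, in arms with a different dose range. The documents give nothing from which to size that.

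The text available to me ends within the Section 5.1 schedules, so I could not check whether Section 8 or the SAP already derives etiology from baseline serology.

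**What to change.** **Criteria.** Reconcile 2(f) with 2(h) so that each combination of HBsAg, HBeAg, HBV DNA and HCV RNA maps to exactly one cohort. For the noninfected arm, wording consistent with 2(g) would replace 'and/or' with 'and'. HBeAg must also be addressed, or isolated HBeAg positivity stays in both cohorts. The passages on antiviral entry and antiviral continuation, one tied to infection status and the other to cohort enrolment, should be reconciled at the same time. Which rule is right is for the sponsor's clinical team.

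**Analysis.** Section 3.1 closes Expansion enrolment on activation of Amendment 8, so rewording alone will change little. Keep the as-enrolled cohort as primary. Add a sensitivity analysis of ORR and hepatic safety with etiology derived from the screening serology listed in Table 5.1-1, and report how many subjects change group. Keep prior-sorafenib status separate in that analysis. Otherwise a sorafenib-naive subject would be moved into an HBV Expansion group whose criteria require prior sorafenib. For the same reason, serology should not become the primary grouping.

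**Cost.** A short text correction, one derived variable and a few extra tables, with no new data. The downside is that a few subjects may appear in different groups in the primary and sensitivity results, which will need a footnote.

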### 3. Age and Reproductive Status

- a) Males and Females, age 18 or older
- b) Women of childbearing potential (WOCBP) must have a negative serum or urine pregnancy test (minimum sensitivity 25 IU/L or equivalent units of HCG) within 24 hours prior to the start of study drug.
- c) Women must not be breastfeeding.

- d) Males who are sexually active with WOCBP must agree to follow instructions for method(s) of contraception for the duration of study treatment with nivolumab and 7 months after the last dose of study treatment {i.e., 90 days (duration of sperm turnover) plus the time required for the investigational drug to undergo approximately five half-lives.}.
- e) Azoospermic males and WOCBP who are continuously not heterosexually active are exempt from contraceptive requirements. However they must still undergo pregnancy testing as described in this section.
- f) Women of childbearing potential (WOCBP) must agree to follow instructions for method(s) of contraception for the duration of study treatment with nivolumab and 5 months after the last dose of study treatment {i.e., 30 days (duration of ovulatory cycle) plus the time required for the investigational drug to undergo approximately five half-lives.}.

Investigators shall counsel WOCBP and male subjects who are sexually active with WOCBP on the importance of pregnancy prevention and the implications of an unexpected pregnancy. Investigators shall advise WOCBP and male subjects who are sexually active with WOCBP on the use of highly effective methods of contraception. Highly effective methods of contraception have a failure rate of < 1% per year when used consistently and correctly.

At a minimum, subjects must agree to the use of one highly effective method of contraception as listed below:

